22.2 Appendix 2. "Minimal Transthoracic Echocardiography Protocol"

Minimum transthoracic echocardiographic protocol: recommendations of the Eurasian Association of Specialists in Ultrasound and Functional Diagnostics

B.V. Blagodir

Recommendations adopted on 27.09.2018. (voting protocol No. 1 from 28.09.2018).

1. Introduction.

Recent advancements in echocardiography have facilitated the integration of new principles and methodologies into the routine work of an echocardiographer. This necessitates the implementation of a minimal echocardiographic protocol to ensure the quality collection of necessary data, improve quality, and standardize the performance of transthoracic echocardiographic examinations. The Eurasian Association of Ultrasound and Functional Diagnostics Specialists (EAUD) organized on 27.09.2018. The forum 'Ural Echocardiographic Protocol,' where 44 specialists unanimously voted for its adoption.

EAUD offers a minimal step-by-step protocol for comprehensive echocardiographic examination to obtain the most detailed information about the heart, its structures, and the assessment of cardiac function. When pathological morphological and/or functional abnormalities are detected, additional data is required, which is not included in this guideline and will be considered in subsequent guidelines.

2. Requirements for the ultrasound device.

- *2D mode with Tissue Harmonic Imaging (THI)*
- *Standard M-mode*
- *CFD*
- *PWD*
- *CWD*
- *TDI-PW*
- *ECG module for image synchronization and highly accurate verification of the corresponding phase of the cardiac cycle.*

3. Preparation for the study.

[figure not shown]
- a. Familiarize yourself with the referral, indications, and diagnosis.
- b. Preparation of equipment: electrodes, ultrasound gel, clean bed linen, sensor.
- c. Familiarize yourself with the medical documentation and previous echo reports for comparison.
- g. Enter the patient's data into the ultrasound device, check the name, date of birth, height, weight, and medical record number.
- d. Ask the patient to lie down on the couch, attach 3 ECG electrodes, and adjust the height of the couch.
- e. Start scanning with either the left or right hand.
 - It depends on the features of the echo lab and/or personal preferences. It's better to be proficient with both hands.
 - Scanning with the right hand – the patient lies with their back to you. The patient's body should be embraced with the hand. The patient can lean on you. For the right hand, this is a comfortable position, as it relieves tension. This position may be suboptimal in the operating room, in case of injury, as well as in cases of hygiene issues with the patient.
 - Examination with the left hand – the patient is lying face towards you. The hand is placed on the couch. The patient requires a pillow behind their back. This position provides better visibility of the sensor and the patient's chest, allowing contact with it. This position is not optimal if the patient has a cough, so if they are not wearing a mask, you need to provide one for yourself.
- f. Patient position.
 - Subcostal access – the patient lies on their back.
 - Suprasternal access – the patient lies on their back, chin up, and turns their head slightly to the left.
 - Right parasternal access – the patient lies on their right side.

4. Duration of the study.

The average duration of one study, including patient preparation, familiarization with medical documentation, obtaining images, quantitative calculations, and report writing, is 40-45 minutes. However, for a complete study, some patients require more time to obtain additional information, while others require less time.

Section (mode)	Measurements	Exclude	Image
-------------------	--------------	---------	-------

LAX LV (2D)	
At the end of diastole:
 
a. Right ventricle RVWTd, RVOTprox. IVSd, LVIDd, LVPWd.
 
b. Left ventricle: IVSd, LVIDd, LVPWd, LVmass, RWT.
 
At the end of systole: LVIDs, LA diam
 
Note:
 
 1. The linear dimensions of the left ventricle are measured just beyond the ends of the mitral valve leaflets. 2. EF LV by Teicholz can be used to assess the overall contractile function of the left ventricle only in the absence of 	
 • chamber dilation • wall thickening • contractility impairment • valve anomalies. • Left ventricular hypertrophy • Normal values: 
RVWT (1 – 5 mm) RVOTprox (20 – 30 mm) IVS (female 6-9 mm; male 6-10 mm) LVIDd (female 37.8-52.2 mm; male 42.0-58.4 mm) PWT (female 6-9 mm; male 6-10 mm) LVIDs (female 21.6-34.8 mm; male 25.0-39.8 mm) LA (female 27 – 38 mm; male 30 – 40 mm) LVmass (female 67-162 g, male 88-224 g) RWT (≤ 0.42) EF LV 53-73%
	
	local contractility disorders!		

LAX Ao (2D)	
In mid-systole: LVOT diam – I-I method AoAnnulus – I-I method
 
Note: LVOTdiam measurement is conducted proximal and parallel to the plane of the aortic valve from the inner edge of the septal endocardium to the inner edge of the anterior leaflet of the mitral valve within 5-10 mm from the aortic valve.
 
At the end of diastole: AoSinus (L-L method) STJ (L-L method) AoAsc prox (L-L method)
	
 • LVOT obstruction • Aortic dilation • Aortic calcification • Aortic dissection 
Normal values:
 
LVOTdiam (18-22 mm) AoAnnulus (female 22-25 mm, male 23-29 mm) AoSinus (female 27-33 mm, male 31-37 mm) STJ (female 23-29 mm, male 26-32 mm) AoAsc prox (female 23-31 mm, male 26-34 mm)
	  
------------------------	---	--	--

[figure not shown]
[figure not shown]
[figure not shown]

Study protocol

LAX LV (M-mode)	M-mode at the level of the mitral valve: DE amp EF slope EPSS	
Contractility impairment/ dyssynchrony/ paradoxical motion.Mitral valve prolapse.Early closure of the mitral valve (indicates increased left ventricular end-diastolic pressure – LVEDP).Hemodynamic compromise in the presence of exudative pericarditis. 
Normal values: DEamp 18-28 mm EF slope 70-150 mm/sec EPSS \leq 8 mm
	
	M-mode at the level of the Valsalva sinuses: AVOA	
Restriction of aortic valve openingEarly opening of the aortic valveMid-systolic closure of the aortic valve 
Normal values: AVOA 15-26 mm
	
LAX LV (CFD)		
LVOT obstructionaortic stenosisaortic regurgitationmitral stenosismitral regurgitationVentricular septal defect	

[figure not shown]
[figure not shown]
Study protocol

LAX RVIT (2D)	Diameter of the coronary sinus (CS)	
• prolapse/elongation of the leaflets• myxomatous / thickening / calcification with / without restriction of excursion• flailing tricuspid valve leaflet dilation of the tricuspid valve annulus• dilation of the coronary sinus 
Normal values: CS diam (4-10 mm)
	
LAX RVIT (CFD)		Evaluate the flow from the left atrium to the left ventricle 
• tricuspid stenosis• tricuspid insufficiency	
LAX RVIT (PWD)	VE VA	Right ventricular filling pattern	

Study protocol

LAX RVIT (CWD)	TV Vmax TR Vmax	
• Tricuspid stenosis• Tricuspid insufficiency• Calculate RVSP/SPAP 
Normal values: TV Vmax 30-70 cm/s TRVmax \leq 2.5 m/s RVSP/SPAP \leq 25 mm Hg
	
LAX RVOT (2D)	RVOTdistal MPAdiam [*] RPAdiam ^{**} LPAdiam ^{**}	
• Dilation of the right ventricle• RVOT obstruction• Subvalvular pulmonary stenosis• Semilunar prolapse	
		
• pulmonary valve• Thickening/calcification of the pulmonary valve cusps with/without restriction of mobility• Dilation of the pulmonary artery• Narrowing of the pulmonary artery (supravalvular pulmonary stenosis)	

LAX RVOT (M-mode)	
Amplitude of the a-wave
 
Note:
 
Normally, the a-wave is present on the motion graph of the right posterior cusp. Amplitude of the a-wave is 2.7 mm.
 
Absence or reduction of the amplitude of the a-wave < 2 mm, mid-systolic closure (W-flight) indicates the presence of pulmonary hypertension
	
Pulmonary hypertension
	 
LAX RVOT (CFD)		
 • Pulmonary stenosis • Pulmonary regurgitation • Patent ductus arteriosus (PDA) 
Note: Moderate pulmonary regurgitation is a variant of normal.
	

Study protocol

LAX RVOT (PWD)	Vmax RVOT PGmax RVOT	RVOT obstruction	
LAX RVOT (CWD)	PV Vmax PV Gmax PV Gmean PVA EDPR	
 Pulmonary stenosis Pulmonary regurgitation Pulmonary hypertension 
Normal values: PV Vmax 60-90 cm/s EDPR 0-5 mm Hg
 
Note: An increase in EDPR of more than 5 mm Hg indicates the presence of pulmonary hypertension.
	
SAX BASE (2D)	RVOTprox RVOTdistal MPA diam* RPA diam** LPA diam** <small>*if the diameter of the MPA is greater than that of the Ao **as needed</small>	
 Dilation of the right ventricle Prolapse/elongation Myxomatous/thickening/calcification of the tricuspid and pulmonary valves with/without restriction of excursion Flailing TV leaflet Dilation of the TV annulus (TVannulus) RVOT obstruction 
Normal values: RVOTprox 21-30 mm RVOTdistal 17-27 mm
	

SAX BASE (CFD)		
 • Tricuspid stenosis • Tricuspid regurgitation • Pulmonary stenosis • Pulmonary regurgitation • RVOT obstruction • Ventricular septal defect • Atrial septal defect 	
		
 • Elongation and bulging of the atrial septum • Atrial septal aneurysm 	
SAX BASE (CWD)	TV Vmax TR Vmax TVA PV Vmax PV Gmax PV Gmean PVA EDPR	
 • Tricuspid stenosis • Tricuspid regurgitation • Pulmonary stenosis • Pulmonary regurgitation • RVOT obstruction 	
SAX BASAL/MV (2D)	MVA (planimetry)	
 • Prolapse/elongation of leaflets. • Myxomatous/thickening/calcification with/without restriction of excursion. • Local contractility disorder at the basal level 	 

Study protocol

SAX LV (MID/APEX) (2D)		Hypo-, a-, dyskinesia of the walls. Dilation of the right ventricle	
---------------------------------------	--	--	--

Study protocol

A4CV (2D)	
EDVi ESVi EF LV LAVi RVD1 RVD2 RAsax RALax RAA RAVi
 
Normal values: EDVi (female <61 ml/m², male <74 ml/m²) ESVi (female <24 ml/m², male <31 ml/m²) EF LV (female >52%, male >54%) LAVi (<34 ml/m²) RVD1 (25-41 mm) RVD2 (19-35 mm) RALax (<53 mm) RAsax (<44 mm) RAA (<18 cm²) RAVi (female 15-27 ml/m², male 18-32 ml/m²)
 
Note: LAV is calculated using the disk summation method RAV is calculated using the area-length method
		
A4CV (M-mode)	
TAPSE
 
Normal value: TAPSE >17 mm
	
Right ventricular dysfunction
	

A4CV (CFD)		
• Mitral stenosis• Mitral regurgitation• Tricuspid stenosis• Tricuspid regurgitation• Atrial septal defect• Ventricular septal defect	
A4CV (PWD)	VE MV VA MV E/A MV DT MV Adur VE TV VA TV E/A TV DT TV S D ARdur	
• Diastolic dysfunction of the left ventricle• Diastolic dysfunction of the right ventricle 
Normal values: E/A MV 1.0-1.5 DT MV 160-220 msec S>D AR<150 msec Adur<ARdur
	
A4CV (CWD)	MV Vmax MR Vmax MVA TV Vmax TR Vmax TVA RVSP/SPAP	
• Mitral stenosis• Mitral regurgitation• Tricuspid stenosis• Tricuspid regurgitation• Pulmonary hypertension	

Study protocol

A4CV (TDI PW)	e' lat E/e' lat e' med E/e' med E/e' avg	Diastolic dysfunction of the left ventricle Normal values: e' lat >10 cm/s e' med >7 cm/s E/e' lat <13 cm/s E/e' med <15 cm/s E/e' avg <14 cm/s	
A5CV (2D)		
• Mitral stenosis• SAM with/without LVOT obstruction• Aortic sclerosis/stenosis• Dilation of chambers• Local contractility of the ventricular walls	
A5CV (CFD)		
• LVOT obstruction• Mitral stenosis• Mitral regurgitation• Aortic stenosis• Aortic valve insufficiency• Ventricular septal defect	
A5CV (CWD)	MV Vmax MR Vmax MV PHT AoV Vmax AR PHT LVOT Vmax TV Vmax TR Vmax RVSP/SPAP	
• LVOT obstruction• Mitral stenosis• Mitral regurgitation• Aortic stenosis• Aortic valve insufficiency	

Study protocol

3C (2D)		
 Dilation of chambers Reduced contractility Left ventricular hypertrophy LVOT obstruction 	
3C (CFD)	MV Vmax MR Vmax AoV	
Pathology of the mitral and aortic valves Aortic aneurysm
 
 Mitral stenosis Mitral regurgitation Aortic stenosis Aortic regurgitation LVOT obstruction 	
3C (PWD)	LVOT Vmax	LVOT obstruction	
3C (CWD)	MV Vmax MR Vmax MVA AoV Vmax AR PHT AVA	
 Mitral stenosis Mitral regurgitation Aortic stenosis Aortic valve insufficiency 	

2C (2D)	EDVi ESVi EF LV LAVi	
 Dilation of chambers Dilation of the DAO Thrombosis of the left atrial appendage Local contractility disorder Reduced contractility of the left ventricle 	
--------------------	-------------------------------	---	--

2C (CFD)		
 Mitral stenosis Mitral regurgitation 	
2C (CWD)	MV Vmax MR Vmax MVA	
 Mitral stenosis Mitral regurgitation 	
3C RVIT (CFD, CWD)	TV Vmax TR Vmax RVSP/SPAP	The best section that provides the ideal Doppler angle for assessing tricuspid regurgitation and calculating RVSP/SPAP in cases where other sections had a suboptimal Doppler angle.	

[figure not shown]
[figure not shown]
[figure not shown]

Study protocol

Sub A4CV (2D)	RVWT	
• Right ventricular hypertrophy• Pericardial effusion• Lipohypertrophy of the interatrial septum• Hemodynamic compromise in tamponade	
Sub A4CV (CFD)		
• Atrial septal defect• Ventricular septal defect• Mitral regurgitation• Tricuspid insufficiency	
Sub SAX BASE (2D, CFD)		
Atrial septal defect (ASD)
 
Note: This is the ideal section for assessing the atrial septal defect, as it provides the ideal Doppler angle.
	

Study protocol

Sub IVC (2D / M-mode)	IVC diam insp IVC diam expir	
Dilation of the inferior vena cavaAssess the inspiratory collapse of the inferior vena cavaDetermine the right atrial pressure (RAP) (RAP = 3/8/15). 
Note: IVC diameter according to the ASE guidelines is measured at the entry proximal to the hepatic vein.
 
Normal values: IVC diam expir (12-21 mm).
	 
Sub DAO (2D)	DAO diam	
DilationAneurysmDissectionAtherosclerosis 
Normal values: DAO diam (<30 mm).
	

Study protocol

Sub DAO (PWD)	PSV AT	
• Distal effects of aortic coarctation• Distal effects of aortic stenosis 
Normal values AT <80 msec Hemodynamically significant proximal events: AT \geq100 msec.
	
Supra LAX (2D)	AAo diam AoArch diam DAO prox	
• Aneurysm• Dissection• Atherosclerosis• Coarctation	
Supra LAX (CFD / PWD)	PSV AAo PSV DAO	
Dissection Coarctation
 
Normal values: PSV AAo (< 200 cm/s) PSV DAO (<200 cm/s)
	

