7. PROTOCOL SYNOPSIS

Study Title	Assessment of the left ventricle reverse remodeling outcomes in patients with aortic valve insufficiency after surgical correction
Sponsor	Investigator-Initiated Study
Study Phase	Phase III
Hypothesis	We hypothesize that surgical correction of functional mitral regurgitation during interventions for chronic aortic valve insufficiency in patients with significant dilatation of the left heart chambers affects the reverse remodeling of the left ventricle in the postoperative period.

Research objectives and tasks	
Research objective:
 
To assess myocardial reverse remodeling in patients with significant left ventricular dilation caused by chronic aortic regurgitation, depending on the degree of mitral valve insufficiency and surgical approach.
 
Main objectives of the study:
 
1. To evaluate the short-term and long-term outcomes of aortic valve replacement for aortic valve insufficiency in patients with significant left ventricular dilation2. To compare the results of myocardial reverse remodeling depending on the strategy regarding functional mitral valve insufficiency at 3 and 12 months post-surgery3. To determine preoperative predictors of an unfavorable left ventricle function and architecture recovery prognosis.4. Assess the patients life quality 12 months after surgery5. Develop a clinical protocol for simultaneous surgical treatment of mitral regurgitation during aortic valve replacement in patients with significant left ventricular myocardial remodeling caused by chronic aortic regurgitation
Study design	This study is a multicenter, comparative, prospective

Inclusion criteria	
1. Age over 18 years2. Proposed primary elective surgical intervention for chronic aortic regurgitation3. Presence of functional mitral regurgitation4. Left Ventricular End-Diastolic Volume 250 ml\geq
Exclusion criteria	
1. Infectious endocarditis2. Previous myocardial infarction3. Necessity for simultaneous myocardial revascularization4. Acute aortic regurgitation5. Previously established left ventricular dilation not associated with the development of aortic regurgitation6. Lack of informed consent
Number of study subjects	120 patients

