10.2 Study endpoints

Primary endpoints:

1. *Reduction of the left ventricle end-diastolic volume at 3 and 12 months after surgical correction of aortic regurgitation*
2. *Freedom from readmission for heart failure related conditions 12 months after surgery*

Secondary endpoints:

1. Patient quality of life according to the EQ-5D-5L questionnaire results.

Exploratory endpoints:

1. Left ventricle ejection fraction at 3 and 12 months after surgical correction of aortic regurgitation

2. Diastolic function of the left ventricle based on echocardiography results, assessed preoperatively and at 3 and 12 months after surgical correction of the aortic regurgitation (mean E/e', DT)
3. Indexed to BSA volume of the left atrium (according to transthoracic echocardiography results) preoperatively, as well as at 3 and 12 months after surgical treatment

*BSA – body surface area, calculated using the Mosteller formula

11. Study design

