12.4.6 ECHO-cardiography

ECHO-cardiography will be performed as part of Examinations 1-5. It is planned to perform transthoracic ECHO-cardiography and transesophageal intraoperative ECHO-cardiography. The scope of the study during Examinations 1, 3-5 will correspond to the minimum transthoracic EAUD protocol (https://easud.org/sites/default/files/manuals/tte_protokol_eaud.pdf). Examination 2 may be significantly hindered due to unsatisfactory visualization. All DICOM images obtained during the examination of each study participant will be stored in RAW format on a common DICOM server for all research centers. A selective cross-analysis of the standardized set of DICOM data, in accordance with EAUD, is planned to be conducted by physicians with more than 5 years of experience in cardiovascular imaging in the ultrasound modality.

- *The assessment of myocardial contractility will be performed using the Simpson Biplane method, the General Electric “auto EF” algorithm, and Speckle Tracking analysis based on General Electric algorithms.*
- *The standard transthoracic protocol in all cases will be supplemented by myocardial strain analysis with the recording of initial RAW DICOM data, as well as Global Longitudinal Strain, Strain Rate, and myocardial mechanical dispersion.*

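### As the protocol is written, the 3- and 12-month EDV may be measured after the operator has read the earlier echo reports and the operative record

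*Protocol*

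**What the plan says.** Section 10.2 gives as the first primary endpoint: "Reduction of the left ventricle end-diastolic volume at 3 and 12 months after surgical correction of aortic regurgitation". The synopsis (section 7) states the comparison it serves: "To compare the results of myocardial reverse remodeling depending on the strategy regarding functional mitral valve insufficiency at 3 and 12 months post-surgery".

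Section 12.4.6 sets how the echo is done: "The scope of the study during Examinations 1, 3-5 will correspond to the minimum transthoracic EAUD protocol". Appendix 2 (22.2) reproduces that guideline. Under its item 3, preparation for the study, step a reads "Familiarize yourself with the referral, indications, and diagnosis" and step c reads "Familiarize yourself with the medical documentation and previous echo reports for comparison". Both come before step e, where scanning starts. Item 4 of the appendix treats the examination as one piece of work, counting patient preparation together with "familiarization with medical documentation, obtaining images, quantitative calculations, and report writing, is 40-45 minutes".

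The only second look at the images is in section 12.4.6: "A selective cross-analysis of the standardized set of DICOM data, in accordance with EAUD, is planned to be conducted by physicians". The section goes on to set a minimum length of imaging experience for these readers (over 5 years). The text does not say how the cases are selected, what the second reader may know, or whether the second value replaces the first.

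**The concern.** The endpoint is a difference between two readings of the same ventricle. If the second reading is made with the first in view, it can be drawn towards that value, or towards the change the operator expects, and the difference is distorted. At 3 and 12 months the medical documentation would normally also show what was done to the mitral valve, which is the exposure under comparison. A reading influenced by that knowledge can differ between strategies when the ventricles do not.

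The study is a non-randomised cohort and relies on propensity score matching (section 7, statistical methods). Matching balances measured baseline characteristics. It does nothing about error introduced when the outcome is measured, and no later analysis can recover a reading that was never taken independently.

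The point does not rest on silence about masking, which a separate imaging manual or analysis plan could fill. It rests on an instruction the protocol does contain, written for routine care and carried over to the endpoint visits without an exception.

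**Working it through.** **Tracing the text**

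1. Endpoint: EDV reduction at 3 and 12 months (section 10.2). Table 1 places these at Examinations 4 and 5, both with echocardiography.
2. Procedure: Examinations 4 and 5 fall within the range for which section 12.4.6 refers to the EAUD protocol.
3. Order of work: in Appendix 2, item 3, the records and earlier reports are read at step c and scanning begins at step e.
4. Same person: item 4 counts record review, imaging and quantitative calculations within one study, so the operator who has read the records also measures.
5. Content of the records: by Examination 4 there are earlier echo reports (Examinations 1 to 3) and an operation; by Examination 5 the 3-month report is added.
6. Exception: none is stated in 12.4.6, 10.2 or Appendix 2.

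Followed as written, the text allows exposure to both the earlier EDV and the strategy.

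**What anchoring does to the contrast**

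Let R be the true reduction, and let the follow-up reading be pulled a fraction k of the way back to the earlier value. The recorded reduction is (1 − k)R.

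- If k is the same in both strategies, the recorded difference in mean reduction is (1 − k) times the true one. It shrinks towards zero and favours neither strategy.
- If k differs (k1, k2) and R is equal, the recorded difference is (k2 − k1)R, which is spurious.

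The documents give no value for k, so neither case can be sized from them.

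**What a differential error would cost, on assumptions**

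The synopsis gives a target difference of 15 ml/m², 80% power, 5% alpha and at least 64 per group, but no SD. With two-sided alpha, the SD that 64 implies is

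SD = 15 × √(64/2) / (1.960 + 0.842) ≈ 30 ml/m².

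As a check, SD 30 gives 63 per group by the normal formula and 64 by the t-test version. With SD 30 assumed, SE = 30 × √(2/64) = 5.30 ml/m². For an assumed reading bias b between strategies:

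- False-positive rate with no true difference = Φ(b/SE − 1.96) + Φ(−b/SE − 1.96).
- Power when the bias opposes a true 15 ml/m² ≈ Φ((15 − b)/SE − 1.96).

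| b (ml/m²), assumed | b as share of 15 | False-positive rate | Power, bias opposing |
|---|---|---|---|
| 0 | 0% | 5.0% | 80.7% |
| 1.5 | 10% | 5.9% | 72.1% |
| 3 | 20% | 8.7% | 61.9% |
| 5 | 33% | 15.6% | 47.0% |
| 7.5 | 50% | 29.3% | 29.3% |

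The table shows sensitivity only. Nothing in the protocol says which row applies, and b = 0 is not excluded. The synopsis also states the 15 ml/m² for left ventricular volumes without naming EDV.

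**The case against.** **Scope.** Section 12.4.6 adopts the scope of the EAUD protocol, which most naturally means its views and measurements. Step c sits among general preparation notes, beside bed linen and couch height. A reader might infer that every follow-up reading will be made with the earlier value in view. The text does not support that: it permits and prompts such readings but nowhere requires the endpoint to be measured after the reports are read. What remains is that Appendix 2 is the only operator procedure given and nothing sets step c aside.

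**Method.** A reader might also infer that EDV is traced by hand and so easily swayed. Section 12.4.6 names Simpson biplane, an automated ejection fraction algorithm and speckle tracking, all under contractility, and does not say which supplies the endpoint EDV. Manual tracing is partly inference; equally, nothing makes an unedited automated value the endpoint.

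**Direction.** The hypothesis in the synopsis has no direction, and sections 9.3 and 11.1 argue both for and against residual mitral regurgitation. No shared expectation favouring one strategy is shown. Anchoring of equal strength in both groups would only dilute the contrast. This stands: differential bias is a possibility, not a demonstrated fact.

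**Size.** A tempting illustration takes a 3% to 10% reading shift on 250 ml (7.5 to 25 ml), divides by a body surface area of 1.9 m² (3.9 to 13.2 ml/m²), and reports 26% to 88% of the 15 ml/m² target. It cannot be relied on. The shift and the body surface area are assumed, and 250 ml is the preoperative entry threshold, not a postoperative volume.

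**Clinical value.** Comparison with earlier studies is useful in postoperative patients. This stands, so the remedy should postpone access, not remove it.

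**Conclusion.** The point holds as a risk of bias created by the written procedure. The 3- and 12-month EDV may be measured with knowledge of the earlier EDV and of the mitral strategy, because the routine-care step applies to these visits through section 12.4.6 and no exception is made for the endpoint. This can anchor the change score and may bias the comparison between strategies.

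The amount cannot be estimated from the documents. The table under working is conditional on an SD of 30 ml/m², 64 per group, two-sided 5% and an assumed bias. It supports only the statement that a differential error well below 15 ml/m² would matter.

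The conclusion assumes that operators follow Appendix 2 as reproduced and that no separate instruction withholds the reports. It should be corrected because the remedy is cheap and the bias could not be removed by analysis afterwards. It does not by itself invalidate the design.

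**What to change.** Add to section 12.4.6:

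1. **On-site reading.** Step c of the Appendix 2 preparation list does not apply to the endpoint measurement. At Examinations 4 and 5, EDV is measured and recorded with a time stamp in the primary documentation before the previous echo reports and the operative record are opened. They are available straight afterwards for clinical comparison. The value is then transferred to the individual registration card, in the order and within the 5 days that section 17.1 requires.
2. **Cross-analysis.** Run the selective cross-analysis already planned on the stored DICOM files with patient, visit, strategy and first reading removed. Draw the cases at random from both strategies and both centres. Report agreement with the on-site EDV separately by strategy; a gap between strategies would signal differential reading.
3. **Limits, stated in the text.** The on-site operator knows which visit it is. A mitral ring or prosthesis may be visible, so masking to strategy is partial in both readings. The cross-analysis covers a sample, so it can detect differential reading but does not correct the endpoint.

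Cost: a short protocol amendment, which section 15.1 requires to be agreed with the principal investigator and the local ethics committee; de-labelling on the existing DICOM server; and a slightly slower workflow at two visits. No new scan or additional reader is needed.
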